10.3.2. Adverse Drug Reaction

An adverse drug reaction is any untoward and unintended response in a participant to an IMP which is related to any dose administered to that participant.

'Response' in this context means that a causal relationship between a medicinal product and an AE is at least a reasonable possibility.

All AEs assessed by either the reporting PI/investigator or the sponsor as having a reasonable causal relationship to an IMP qualify as adverse drug reactions. The expression 'reasonable causal relationship' means to convey in general that there is evidence or argument to suggest a causal relationship.

10.3.3. Unexpected Adverse (Drug) Reaction

An "Unexpected Adverse (Drug) Reaction" means an adverse reaction, the nature and severity of which is not consistent with the information about the medicinal product in question set out:

- (a) In the case of a product with a marketing authorisation, in the Summary of Product Characteristics for that product,
- (b) In the case of any other IMP, in the Investigator's Brochure relating to the study in question.

10.3.4. Serious Adverse Event

SAE Definition
An SAE is defined as any untoward medical occurrence that, at any dose:
a. Results in death
b. Is life threatening

The term 'life threatening' in the definition of 'serious' refers to an event in which the participant was at risk of death at the time of the event. It does not refer to an event, which hypothetically might have caused death, if it were more severe.

c. Requires inpatient hospitalisation or prolongation of existing hospitalisation

 • In general, hospitalisation signifies that the participant has been detained (usually involving at least an overnight stay) at the hospital or emergency ward for observation and/or treatment that would not have been appropriate in the physician's office or outpatient setting. Complications that occur during hospitalisation are AEs. If a complication prolongs hospitalisation or fulfils any other serious criteria, the event is serious. When in doubt as to whether "hospitalisation" occurred or was necessary, the AE should be considered serious. • Hospitalisation for elective treatment of a pre-existing condition that did not worsen from baseline is not considered an AE.
d. Results in persistent disability/incapacity

 • The term disability means a substantial disruption of a person's ability to conduct normal life functions. • This definition is not intended to include experiences of relatively minor medical significance such as uncomplicated headache, nausea, vomiting, diarrhoea, influenza, and accidental trauma (e.g., sprained ankle) which may interfere with or prevent everyday life functions but do not constitute a substantial disruption.
e. Is a congenital anomaly/birth defect
f. Is an important medical event

 • Important medical events' – some medical events may jeopardise the participant or may require an intervention to prevent one of the above characteristics/consequences. Such events should also be considered as 'serious' in accordance with the above definition. • Medical judgement should be exercised in deciding whether an adverse event/reaction is serious. Important adverse events/reactions that are not immediately life threatening or do not result in death or hospitalisation but may jeopardise the participant or may require intervention to prevent one of the other outcomes listed in the definition above occurring, should also be considered serious. Details of the SAE must be provided.

10.3.5. Suspected Unexpected Serious Adverse Reaction

A SUSAR is a serious adverse reaction, the nature and severity* of which is not consistent with the information about the medicinal product in question, as defined in the Investigator's Brochure relating to the study in question.

Medical events will be assessed for expectedness against the reference safety information section of the Investigator's Brochure or equivalent, and any available Investigator's Brochure addendum. Any changes to the reference safety information will be deemed as a change to the risk/benefit profile and will require a substantial amendment to be submitted to the MHRA. This amendment must be approved before the changes are implemented in the study.

*The term 'severity' is used here to describe the intensity of a specific event. This is not the same as 'serious' which is based on participant/event outcome or action criteria.

10.3.6. Recording, Assessment, and Follow-up of Adverse Events/Serious Adverse Events

10.3.6.1. Adverse Event/Serious Adverse Event Recording

All AEs/SAEs will be collected from the time of written study-specific informed consent until study completion/final study contact or until the resolution of the AE. Adverse events will be fully recorded in the source documents as they are reported whether spontaneously reported by a participant or in response to questioning about wellbeing at each face-to-face study visit and during telephone calls. Enquiries about AEs should cover the period between the previous and current visit.

The following are examples of open-ended, non-leading questions that may be used to obtain this information:

- How are you feeling?
- Have you had any medical problems since your last visit/assessment?
- Have you taken any new medicines, other than those given to you in this study, since your last visit/assessment?

Following the reporting of AEs and concomitant medication, the PI/investigator should assess the participant's eligibility to continue in the study.

The PI/investigator will record all relevant information regarding an AE/SAE in the source documents and evaluate AEs/SAEs using the following guidelines:

- Description of event (if the event consists of a cluster of signs and symptoms, a diagnosis should be recorded)
- Seriousness
- Grade (or severity)
- Onset date and time
- Frequency

- Date and time of resolution (or 'continuing' if unresolved)
- Action taken
- Concomitant medication
- Clinical outcome
- Relationship or causality (IMP/challenge agent/study procedures/concomitant medication/other).

Any clinically significant abnormal laboratory result, vital sign or other measure will be followed until resolution (return to normal or baseline values), stabilisation, it is judged by the PI/investigator to be no longer clinically significant, the participant is lost to follow-up, or an alternative explanation has been provided.

If an AE is not resolved at the end of the study, the AE should be followed until it has resolved or (in the case of pregnancy) the pregnancy has been terminated (including spontaneous abortion), resulted in a birth, or a decision has been made by the sponsor that no further follow-up is required.

Even if the AE/SAE is assessed by the PI/investigator as not reasonably attributable to the challenge agent, its occurrence must be fully documented in the source notes.

10.3.6.2. Assessment

Description

If the event consists of a cluster of signs and symptoms, a diagnosis should be recorded (e.g., gastroenteritis) rather than each sign and symptom.

Onset and end

The dates and times of the onset and end of the event should be recorded.

Assessment

Challenge Agent-related Symptoms
 
The PI/investigator will assess, and review challenge agent-related symptoms recorded in participants' hVIVO symptom diary cards. Symptoms greater than Grade 0 will be expected and presumed to represent infection consequent to challenge agent inoculation and will not be additionally captured as AEs unless they meet the definition of an AE and are deemed to be clinically significant (in the opinion of the PI/investigator).
 
Following challenge agent inoculation all unexpected (in the opinion of the PI/investigator) symptoms post inoculation will be captured as AEs, along with all other occurrences that meet the criteria for an AE.

Physical Examination
 
Any clinically significant change in complete physical examination findings during the study will be documented as an AE.

Symptom-directed Physical Examination

Following challenge agent inoculation, URT symptoms (nasal discharge, otitis, pharyngitis, sinus tenderness) and LRT symptoms (abnormal breath sounds externally [e.g., stridor, wheezing] and on chest auscultation [rhonchi, crepitations or other]) will be expected and presumed to represent infection consequent to challenge agent and will not be additionally captured as AEs unless they meet the definition of an AE and are deemed to be clinically significant (in the opinion of the PI/investigator).

Vital Signs

Deterioration in a vital sign (compared to baseline) should only be reported as an AE if the deterioration fulfils the criteria for an AE. If deterioration in a vital sign is associated with clinical signs and symptoms, the sign or symptom will be reported as an AE and the associated vital sign will be considered as additional information.

Temperature

Following challenge agent inoculation, pyrexia (temperature $\geq 37.9^{\circ}\text{C}$) will be expected and presumed to represent infection consequent to challenge agent and will not be additionally captured as an AE unless it meets the definition of an AE and is deemed to be clinically significant (in the opinion of the PI/investigator) to be classed as an AE.

Following challenge agent inoculation all unexpected (in the opinion of the PI/investigator) pyrexia will be captured as an AE, along with all other occurrences that meet the criteria for an AE.

Spirometry

A 15% drop in a spirometry value (compared to baseline) confirmed by a repeat on the same day, will be a Grade 1 (mild) AE. The PI/investigator will use his/her clinical judgement to assign severity grades above Grade 1, based on evaluation of clinical signs and symptoms. If the repeated value has returned to normal an AE will not be raised.

Laboratory Values

Deterioration in a laboratory value (compared to baseline) should only be reported as an AE if the deterioration meets the criteria for an AE and is deemed to be clinically significant (in the opinion of the PI/investigator). If deterioration in a laboratory result is associated with clinical signs and symptoms, the sign or symptom will be reported as an AE and the associated laboratory result will be considered as additional information.

The PI/investigator and/or SME will judge whether abnormal laboratory values are clinically significant or not clinically significant, and record this in the source document. This entry should be signed and dated by the relevant PI/investigator. Laboratory abnormalities detected at screening will be considered as part of the medical history and will not be reported as AEs.

Challenge agent associated laboratory abnormalities (e.g., elevated alanine transferase, aspartate aminotransferase, or gamma glutamyl transferase; decreased neutrophils) may be recorded as AEs (at the discretion of the PI/investigator).

C-reactive Protein

Any value above 5 mg/L but less than 60 mg/L will be a Grade 1 (mild) AE (unless deemed non clinically significant by the PI/investigator). The PI/investigator will use his/her clinical judgement to assign severity grades above Grade 1, based on evaluation of clinical signs and symptoms.

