2.3. The Respiratory Syncytial Virus Human Challenge Model

The RSV human challenge model was developed to not only aid understanding of RSV disease, but to also assess the efficacy of RSV antivirals, immunomodulators and vaccines. The RSV-A Memphis 37b challenge strain has been used for over 15 years by both hVIVO and others and has helped assess the efficacy of numerous RSV therapies (as reviewed by [Lambkin-Williams et al, 2018](#); [DeVincenzo et al, 2020a](#); [DeVincenzo et al, 2020b](#); [Stevens et al, 2018](#)) and vaccines ([Sadof et al, 2021](#); [Pfizer 2021](#); [Bavarian Nordic 2021](#)). Specifically, hVIVO have safely and successfully used the RSV challenge strain in over 1400 healthy participants (18 to 60 years of age) including the inoculation of 24 participants between 60 and 75 years of age. Additionally, another clone of the same strain of live RSV (Memphis 37c) has been used as an inoculation agent and was shown to be safe in over 77 healthy young adults across 3 studies. Healthy RSV challenge study participants have approximately 65% to 85% chance of becoming infected with RSV following the administration of the virus ([DeVincenzo et al, 2010](#)). Typical RSV illness is characterised by an abrupt onset of rhinitis, nasal stuffiness, malaise, myalgia (muscle aches), and sore throat. In healthy adults, the illness usually resolves without any treatment, with relief of symptoms occurring naturally within 7 to 10 days. Respiratory syncytial virus, like many viruses, can cause more substantial health issues such as myocarditis (inflammation or damage to the heart muscle). Adults and children present with RSV-related myocarditis rarely, with symptomless occurrences likely going undiagnosed in the community.

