
 To evaluate the safety of multiple orally administered doses of RV299 when compared to placebo. 	
 Safety data including, but not limited to, occurrence of AEs from initial administration of IMP up to the Day 28 follow-up. Occurrence of SAEs from initial administration of IMP up to the Day 28 follow-up.

 To monitor the safety of the challenge virus. 	
 Occurrence of AEs related to the viral challenge from viral challenge (Day 0) up to the Day 28 follow-up. Occurrence of SAEs related to the viral challenge from viral challenge (Day 0) up to the Day 28 follow-up. Use of concomitant medications from viral challenge (Day 0) up to the Day 28 follow-up.

Objectives	Endpoints

Pharmacokinetics
	

 • To characterise the PK profile of RV299 after a single oral dose and after multiple oral doses in plasma from healthy participants inoculated with RSV. 	
Secondary endpoints related to PK include, but are not limited to:
 
 • Time to maximum plasma concentration (t_{max}), terminal half-life ($t_{1/2}$), C_{max}, area under the plasma concentration-time curve from time zero to the end of the dosing interval (AUC_{τ}), AUC_{0-24h}, and area under the plasma concentration-time curve from time zero to infinity ($AUC_{0-\infty}$).

CCI
 	
	
	
	
	
	
	
	
	
	
	
	
	
	
	
	
	
	
	
	
	
	
	
	
	
	
	
	
	
	
	
	
	
	
	
	
	
	
	
	
	
	
	
	
	
	
	
	
	
	
	
	
	
	
	
	
	
	
	
	
	
	
	
	
	
	
	
	
	
[figure not shown] Females of childbearing potential must have a negative pregnancy test prior to enrolment. Females of non-childbearing potential: 
 Post-menopausal females defined as amenorrhea for ≥ 12 months with no alternative medical cause. A high follicle-stimulating hormone (FSH) level, within appropriate post-menopausal range, may be used to confirm post-menopausal state in the absence of combined hormonal contraception or hormone replacement therapy. If there is < 12 months of amenorrhea 2 FSH samples are required at least 4 to 6 weeks apart. Documented status as being surgically sterile (e.g., tubal ligation, hysterectomy, bilateral salpingectomy, and bilateral oophorectomy).

No.	hVIVO APPROVED STANDARD INCLUSION CRITERIA (Viral Challenge Volunteer Studies) Final v11.0, 08FEB2022

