10.3.1. Adverse Event

AE Definition

An AE is defined as any untoward medical occurrence in clinical study participants administered a pharmaceutical (investigational or non-investigation) product. An AE does not necessarily have a causal relationship with the study intervention. An AE can therefore be any unfavourable and unintended sign (including an abnormal laboratory finding), symptom, or disease temporally associated with the use of a medicinal (investigational or non-investigational) product (definition as per ICH).
 
This will also cover any AEs occurring after study intervention(s) including administration with the challenge agent in viral challenge studies.

Unsolicited AEs

Unsolicited AEs are defined as any AEs observed by the participant or PI/investigator which are not pre-listed on the symptom diary card. Unsolicited AEs will be collected upon signature of study-specific ICF until the end of the study. Any unsolicited AEs observed by the PI/investigator and/or reported by the participant must be recorded in the eCRF regardless of causality in relationship with IMP.

Events Meeting the AE Definition

 Exacerbation of a pre-existing illness. Increase in frequency or severity of a pre-existing episodic condition. A condition detected or diagnosed after study intervention administration even though it may have been present prior to the start of the study. A complication that occurs during a hospitalisation. A clinically significant change in laboratory parameter.

Events NOT Meeting the AE Definition

 Medical or surgical procedures (e.g., surgery, endoscopy, tooth extraction, transfusion); the condition that leads to the procedure is an AE. Pre-existing disease or condition present or detected prior to start of study intervention administration that does not worsen (including screening findings such as abnormal laboratory results).

- Hospitalisation for elective surgery, social and/or convenience admissions provided they are arranged before the start of study intervention administration and the reason does not worsen.
- Over-administration of either the study intervention or concomitant medication without any signs or symptoms.
- An uncomplicated pregnancy or an induced elective abortion to terminate a pregnancy without medical reason.
- Typical/normal/solicited viral infection symptoms on symptom diary cards.

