10.7.2.4 Clinical Symptom-Related Endpoints

Area under the Curve over Time of Total Clinical Symptoms (TSS-AUC) as Measured from 10 Symptoms within the Graded Symptom Scoring System Collected 3 Times Daily Starting at Initial Administration of IMP up to Planned Discharge from Quarantine

Total symptom scores (from 10 items of the 13-item symptom diary card) will be used to calculate the AUC, from the assessment nearest to the time of the first administration of IMP (can be prior to or after dosing, depending on whether dosed in the morning or evening), i.e. baseline, until Day 12 (Quarantine discharge), for each participant using the trapezoidal rule [1].

Symptoms are assessed 3 times daily for Day 1 to Day 11 (and once for Day 12) and recorded on the symptom diary cards at each assessment. The following types of symptoms are recorded (on a grading scale, 0 to 3 (or 0 to 4 for the Shortness of Breath symptom)):

- Upper Respiratory Tract (URT): runny nose, stuffy nose, sore throat, sneezing, earache.
- Lower Respiratory Tract (LRT): cough, shortness of breath.
- Systemic: headache, malaise, muscle/joint ache/stiffness.
- Not used for analyses: chilliness/feverishness, chest tightness, wheeze.

A total symptom score will be derived for each participant, separately for each assessment (symptom diary card) on each day (Day 0 to Day 12) as follows:

- For each assessment, sum the 10 observed symptom grade values for each symptom diary card to obtain a total symptom score for each symptom diary card. If the participant does not have all 10 observed values on a specific symptom diary card being considered, then total symptom score will not be calculated for that symptom diary card. It is expected that participants will not have missing data.
- The AUC calculation will be based on the available non-missing calculated total symptom scores between the start and end of the defined AUC time. However, for an AUC to be derived, the participant should have at least 1 non-missing calculated total symptom scores at the start of the AUC period (e.g. date of first dose of IMP) and also at the end of the AUC time period

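### Mild diary symptoms are presumed viral whatever the infection status and are only listed one by one, so no by-arm safety table in the visible SAP could show an RV299-caused headache or malaise

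*Protocol*

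**What the plan says.** Participants complete a 13-item symptom card three times a day in quarantine (Protocol 8.3.2). The items include headache, malaise/tiredness, muscle or joint ache, chest tightness and wheeze.

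On what is recorded as an AE, Protocol 10.3.6.2 states: "Symptoms greater than Grade 0 will be expected and presumed to represent infection consequent to challenge agent inoculation and will not be additionally captured". The same sentence gives an exception: "unless they meet the definition of an AE and are deemed to be clinically significant (in the opinion of the PI/investigator"). The next paragraph adds a second route, for symptoms that the investigator finds unexpected: "symptoms post inoculation will be captured as AEs, along with all other occurrences that meet the criteria for an AE".

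Protocol 10.3.1 lists, among events that do not meet the AE definition, "Typical/normal/solicited viral infection symptoms on symptom diary cards". It also says: "Unsolicited AEs are defined as any AEs observed by the participant or PI/investigator which are not pre-listed on the symptom diary card".

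Participants are dosed whether or not infection is detected: after a positive qicPCR, or from the evening of Day 5 if there is none (Protocol synopsis; SAP 6.1). Protocol 2.3 gives challenged participants "approximately 65% to 85% chance of becoming infected with RSV following the administration of the virus".

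Protocol section 3 sets a secondary safety objective: "To evaluate the safety of multiple orally administered doses of RV299 when compared to placebo". SAP 10.9 meets it with descriptive safety-population summaries of AEs, laboratory values, vital signs, spirometry and ECG. SAP 10.7.2.4 sums ten diary items into a total symptom score for efficacy, lists the individual scores, and says of the other three: "Not used for analyses: chilliness/feverishness, chest tightness, wheeze".

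**The concern.** A challenge trial has good reason not to record every runny nose twice. But the presumption is a statement about cause, and it is applied where cause is what the safety comparison should examine. It covers participants who never become infected, and symptoms that first appear after dosing. For an uninfected participant it is wrong.

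Mild complaints are the ones most likely to be filtered out. Protocol 2.2.1 reports that all AEs in the only earlier RV299 study (32 healthy adults on RV299, data still blinded and pooled with placebo) were mild. A treatment-emergent table with few headaches could then be taken as evidence that RV299 does not cause them, when the recording rule had removed them.

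**Working it through.** The plan states no figure on this point, and the protocol's sample-size section is redacted, so there is nothing to reproduce. The check sets the passages side by side and adds some simple arithmetic.

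**1. Does the presumption apply throughout dosing?** Ten doses 12 hours apart span 9 × 0.5 = 4.5 days. The earliest start, the evening of Day 2, ends on the morning of Day 7 (2.5 + 4.5 = 7.0). The latest start, the evening of Day 5, ends on the morning of Day 10 (5.5 + 4.5 = 10.0). Diary cards run to Day 12, so every dose falls within the diary period. Protocol 10.3.6.2 sets no condition on infection or on timing relative to IMP.

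**2. How many dosed participants would be uninfected?** Inputs: 40 per arm (Protocol synopsis) and an infection rate of 65% to 85% (Protocol 2.3 and Table 2-1).
- At 85%: 40 × 0.15 = 6 per arm, 12 of 80.
- At 65%: 40 × 0.35 = 14 per arm, 28 of 80.

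**3. Which diary symptoms reach the AE tables?** Those judged clinically significant or unexpected. They receive a causality assessment that includes IMP (Protocol 10.3.6.1) and enter the by-arm tables (SAP 10.9.1). Neither route is firmly defined. The first also requires the AE definition to be met, yet Protocol 10.3.1 places solicited diary symptoms outside that definition. The second requires a symptom to be called unexpected, when the preceding sentence has just declared it expected. Capture of a mild symptom therefore rests on judgement without a stated criterion.

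**4. Where do the remaining symptoms go?** In the visible SAP:
- Ten items, headache and malaise among them, enter the total symptom score. It is compared between arms as an efficacy endpoint, so a drug-caused increase and an antiviral decrease net out and no single symptom can be read.
- Individual grades for all 13 items appear in Listing 16.2.6.3.1. No visible safety table uses diary data.

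**5. Do uninfected participants enter the symptom-score comparison?** SAP 13.2 repeats the symptom-score AUC, change-from-baseline AUC and by-assessment tables in ITT when ITT differs from ITT-I by more than one participant in an arm. The chance of at least two uninfected among 40 at 85% infection is 1 − 0.85^40 − 40 × 0.15 × 0.85^39 = 0.988, and it exceeds 0.999 at 75% or 65%. The ITT repeat is close to certain, but it pools infected with uninfected.

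**6. What could a by-symptom comparison show?** Symptom frequencies are not in the documents, so these are assumptions: a 20-point excess on RV299 over a placebo frequency of 5%, 10%, 20% or 50%. Power of a two-sided 5% test of two proportions (pooled variance under the null, unpooled under the alternative):

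| Participants per arm | Power range |
|---|---|
| 40 | 0.45 to 0.72 |
| 14 | 0.18 to 0.31 |
| 6 | 0.10 to 0.15 |

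An uninfected-type subset can support description only.

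**The case against.** Leaving expected challenge symptoms out of the AE data is a deliberate choice. It is applied under blinding, identically in both arms, and the data are kept and listed. That stands, and the point does not ask for AE collection to change.

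Several stronger readings are tempting, but the documents do not support them:
- *All diary symptoms are barred from the AE tables.* They are not. The two routes in Protocol 10.3.6.2 exist, and at the Day 5 evening start the absence of a positive qicPCR is known, which can inform the judgement.
- *The safety tables contain only AEs.* SAP 10.9 also tabulates laboratory values, vital signs (including temperature, oxygen saturation and respiratory rate), spirometry and ECG. Concomitant medications are tabulated by arm (SAP 10.5), so paracetamol given for a headache would appear there. None of these shows a mild untreated headache or malaise.
- *Chilliness/feverishness, chest tightness and wheeze are in no summary at all.* This cannot be established. Protocol 8.3.2 says that they may be explored separately, exploratory sections and some table-list rows are redacted, and Listing 16.2.6.3.3 includes AUCs from all 13 items.
- *Uninfected participants are never compared by arm.* They are in every safety table and in the ITT repeats. Only a separate view of them is absent.

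One further objection shapes the remedy. A subset of participants who fail the laboratory infection criterion would depend on post-dose virology, which an antiviral can change, so the arms would no longer be comparable by randomisation. Status by qicPCR before the first dose avoids this.

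**Conclusion.** The point holds in a limited form. Diary symptoms not judged clinically significant or unexpected stay out of the AE tables whatever the infection status or timing relative to IMP. In the unredacted SAP they can be seen individually only in listings. A mild RV299-caused headache or malaise would show in no by-arm safety table, and its contribution to the symptom score could be cancelled by antiviral benefit.

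About 6 to 14 participants per arm would be uninfected under the same presumption. This assumes that the protocol's infection range applies to the 80 planned participants and splits evenly between arms. The documents give no frequency for drug-caused symptoms and no rate at which investigators would promote them to AEs, so the number missed cannot be estimated. The conclusion concerns the visible text only. This is a gap in reporting that is cheap to close; it does not bias the comparison towards either arm or invalidate the safety analysis.

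**What to change.** Add to SAP 10.9 one descriptive safety-population table. For each of the 13 diary symptoms, give the number and percentage of participants by maximum grade from first IMP to the morning of Day 12, by arm, with the last pre-dose grade shown. Take that grade from a card completed before the first dose, because the symptom-score baseline in SAP 10.7.2.4 may fall after dosing.

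Repeat the table for participants first dosed on the evening of Day 5 without a positive qicPCR. This subset is fixed before dosing. It is not identical to the uninfected group, since some members may turn positive later, so 6 to 14 per arm is only a guide to its size.

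Footnote the treatment-emergent AE tables to say that solicited diary symptoms not judged clinically significant or unexpected are excluded and are shown in the new table.

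The cost is one table shell, its repeat and a footnote, all from data already collected. AE collection is unchanged. The downside is slightly more output, with a repeat that is small and descriptive only.
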